5.3 Dose delays, modifications or discontinuation for non-hematologic side effects

5.3.1 Infection: Subjects who experience an infection requiring intravenous antibiotics will not have

11-H-0134

[name].

01/02/2019 (Amendment HH)

eltrombopag discontinued. If the subject experiences infection severe enough to require vasopressors or intubation, the drug will be withheld until the patient is stable.

5.3.2 Liver function abnormalities: In the event of an increase in the ALT level to > 6 times the ULN, patients will return to clinic or have blood tests drawn by their home physician every 3-4 days. If the ALT remains > 6 times the ULN on a second blood test, eltrombopag will be discontinued until ALT is < 5 times the ULN. Eltrombopag will be restarted at a dose level 50 mg/day lower than the prior dose. If the toxicity appeared on a dose of 25 mg/day, eltrombopag will be discontinued permanently. If liver test abnormalities return to an ALT of > 6 times ULN on this reduced dose, eltrombopag will be permanently discontinued.

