- In ITP subjects, a dose response was seen for eltrombopag doses of 30 mg to 75 mg once daily, with geometric mean $AUC_{(0-\tau)}$ values of 169 $\mu\text{g}\cdot\text{h}/\text{mL}$ for the 75 mg once daily regimen. There was no significant difference between the safety profile of ITP subjects receiving 30, 50 or 75 mg of eltrombopag. Eltrombopag has been examined in a placebo-controlled Phase II study (NCT00102726) in 183 cancer patients receiving carboplatin and paclitaxel. Eltrombopag, 50 mg, 75 mg and 100 mg and placebo (1:1:1:1) was dosed for 10 days after carboplatin and paclitaxel administration for up to 8 cycles in this study; eltrombopag was generally well tolerated as described in the CIB. The eltrombopag geometric mean $AUC_{(0-\tau)}$ values of 191 $\mu\text{g}\cdot\text{h}/\text{mL}$ was observed for

subjects at 100 mg dose group. The study results for the 100 mg group demonstrated that there was evidence for increased platelet production seen in all three eltrombopag arms after the nadir, with a gradual rise in platelet counts from Day 8 to 18 of chemotherapy. No apparent safety issues at 100 mg were identified.

- Thrombocytosis is a theoretical risk of eltrombopag treatment when high dosages are administered. Thrombocytosis has been observed in healthy volunteers as well as in subjects with ITP. None of these subjects experienced an AE related to thrombocytosis. The likelihood that aplastic anemia patients would develop thrombocytosis, given the underlying pathophysiology of their marrow disease, is likely to be low.
- To ensure subject safety, the current study uses a dose escalation scheme in which subjects are exposed to the lowest dose necessary to achieve the desired platelet count or hemoglobin. Only subjects who have tolerated the previous dose will be considered for the next highest dose, dependent on their last platelet count or hemoglobin. This approach minimizes potential risks while allowing the subject the maximum potential for benefit.
- Our group is currently conducting a clinical trial in patients with severe aplastic anemia using a dosing scheme whereby subjects increase doses by 25mg every 2 weeks. Interim results have shown responses in all 3 lineages with low toxicity. All patients reached the maximum dose of 150mg without any reductions in dose necessary. It is anticipated that it would be similar in MAA population with this revised dosing schedule likely to improve responses.

Dose selection after January 8, 2015:

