10.3.1 Promacta® (eltrombopag)

Boxed warnings related to Promacta® (eltrombopag):

WARNING: RISK FOR HEPATIC DECOMPENSATION IN PATIENTS WITH CHRONIC HEPATITIS C
--

RISK OF HEPATOTOXICITY

**See full prescribing information for complete boxed warning
In patients with chronic hepatitis C, PROMACTA in combination with interferon and ribavirin may increase the risk of hepatic decompensation.**

**PROMACTA may increase the risk of severe and potentially life-threatening hepatotoxicity.
Monitor hepatic function and discontinue dosing as recommended.**

Warnings and Precautions:

Hepatic Decompensation in Patients with Chronic Hepatitis C

In patients with chronic hepatitis C, PROMACTA in combination with interferon and ribavirin may increase the risk of hepatic decompensation. In two controlled clinical trials in patients with chronic hepatitis C and thrombocytopenia, ascites and encephalopathy occurred more frequently on the arm receiving treatment with PROMACTA plus antivirals (7%) than the placebo plus antivirals arm (4%). Patients with low albumin levels (less than 3.5 g/dL) or Model for End-Stage Liver Disease (MELD) score greater than or equal to 10 at baseline had a greater risk for hepatic decompensation on the arm receiving treatment with PROMACTA plus antivirals. Discontinue PROMACTA if antiviral therapy is discontinued.

Hepatotoxicity

PROMACTA may increase the risk of severe and potentially life-threatening hepatotoxicity. Measure serum ALT, AST, and bilirubin prior to initiation of PROMACTA, every 2 weeks during the dose adjustment phase, and monthly following establishment of a stable dose. PROMACTA inhibits UDP-glucuronosyltransferase (UGT)1A1 and organic anion-transporting polypeptide (OATP)1B1, which may lead to indirect hyperbilirubinemia. If bilirubin is elevated, perform fractionation. Evaluate abnormal serum liver tests with repeat testing within 3 to 5 days. If the abnormalities are confirmed, monitor serum liver tests weekly until resolved or stabilized. Discontinue PROMACTA if ALT levels increase to greater than or equal to 3 x ULN in patients with normal liver function or greater than or equal to 3 x baseline (or greater than 5 x ULN, whichever is the lower) in patients with pre-treatment elevations in transaminases and are:

- progressively increasing, or
- persistent for greater than or equal to 4 weeks, or
- accompanied by increased direct bilirubin, or

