- accompanied by clinical symptoms of liver injury or evidence for hepatic decompensation.

If the potential benefit for reinitiating treatment with PROMACTA is considered to outweigh the risk for hepatotoxicity, then consider cautiously reintroducing PROMACTA and measure serum liver tests weekly during the dose adjustment phase. Hepatotoxicity may reoccur if PROMACTA is reinitiated. If liver test abnormalities persist, worsen, or recur, then permanently discontinue PROMACTA.

Isolated cases of severe liver injury were identified in clinical trials. The elevation of liver laboratory values occurred approximately three months after initiation of PROMACTA. In all cases, the event resolved following PROMACTA discontinuation.

Thrombotic/Thromboembolic Complications

Thrombotic/thromboembolic complications may result from increases in platelet counts with PROMACTA. Reported thrombotic/thromboembolic complications included both venous and arterial events and were observed at low and at normal platelet counts.

Consider the potential for an increased risk of thromboembolism when administering PROMACTA to

patients with known risk factors for thromboembolism (e.g., Factor V Leiden, ATIII deficiency, antiphospholipid syndrome, chronic liver disease). To minimize the risk for thrombotic/thromboembolic complications, do not use PROMACTA in an attempt to normalize platelet counts. Follow the dose adjustment guidelines to achieve and maintain target platelet counts.

In two controlled clinical trials in patients with chronic hepatitis C and thrombocytopenia, 3% (31/955) treated with PROMACTA experienced a thrombotic event compared with 1% (5/484) on placebo. The majority of events were of the portal venous system (1% in patients treated with PROMACTA versus less than 1% for placebo).

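### The liver dosing rule in section 5.3.2 requires no hold when ALT is between the section 10.3.1 limit and 6 x ULN and direct bilirubin is raised or there is clinical liver injury

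*Combined protocol and SAP*

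**What the plan says.** **Operative rule (section 5.3.2).** "In the event of an increase in the ALT level to > 6 times the ULN", liver tests are repeated every 3 to 4 days. If a second test is still above 6 x ULN, drug is stopped until ALT is below 5 x ULN and then restarted 50 mg/day lower. A permanent stop follows if the toxicity appeared at 25 mg/day, or on recurrence: "If liver test abnormalities return to an ALT of > 6 times ULN on this reduced dose, eltrombopag will be permanently discontinued". Neither bilirubin nor any liver sign or symptom appears in the rule. The off-study criterion for persistent hepatotoxicity in 8.6.2 takes its definition from 5.3.2.

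**Risk text (section 10.3.1).** Under a boxed hepatotoxicity warning, the protocol reproduces the product text: "Discontinue PROMACTA if ALT levels increase to greater than or equal to 3 x ULN in patients with normal liver function", or "3 x baseline (or greater than 5 x ULN, whichever is the lower) in patients with pre-treatment elevations in transaminases", when one of four qualifiers is present. Two of these are a progressive rise in ALT and persistence for at least 4 weeks. The other two are that the rise is "accompanied by increased direct bilirubin" or "accompanied by clinical symptoms of liver injury or evidence for hepatic decompensation". The section also says that the drug inhibits a conjugating enzyme and a transporter, "which may lead to indirect hyperbilirubinemia".

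**Escalation.** Section 5.2 raises the dose of a non-responding adult every 4 weeks to the maximum unless a laboratory value that calls for stopping or dose reduction occurs. Section 2.6 adds a general condition: "Only subjects who have tolerated the previous dose will be considered for the next highest dose".

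**The concern.** ALT together with raised direct bilirubin, or with clinical signs of liver injury, carries information that ALT alone does not. The protocol's own risk section treats that combination as a reason to stop at an ALT well below the level at which 5.3.2 first reacts. In between, the dosing section prescribes nothing, and the escalation table in 5.2 still tells the site to increase the dose of a non-responder.

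The stake is individual safety, during escalation and again in extended access, where 8.6.2 also applies. Much of the interim monitoring is done by home physicians who fax results to the study team, and there an explicit trigger is more dependable than general judgement. Section 10.3.1 also reports isolated severe liver injury with laboratory changes about three months after starting drug. In the current adult scheme the last escalation falls at week 12.

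**Working it through.** No sample size, power or error rate is involved. The check compares thresholds.

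**Inputs.** Section 5.3.2: reaction above 6 x ULN, restart below 5 x ULN. Section 10.3.1: floor of 3 x ULN with normal liver function; with raised baseline, the lower of 3 x baseline and above 5 x ULN. Section 4.2.7: entry allowed with transaminases up to 5 x ULN. Sections 2.6 and 5.2: adult dose 150 to 300 mg in steps of 50 mg every 4 weeks (East Asian 75 to 150 mg in steps of 25 mg). Appendix B: hepatic panel schedule.

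**1. Width of the band.** Write the baseline ALT as b x ULN. With raised baseline the lower limit is min(3b, 5) x ULN. The upper limit is 6 x ULN throughout.

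| Baseline ALT | Lower limit (x ULN) | Band with no required hold (x ULN) |
|---|---|---|
| Normal | 3 | 3 to 6 |
| b = 1.2 | min(3.6, 5) = 3.6 | 3.6 to 6 |
| b = 1.5 | min(4.5, 5) = 4.5 | 4.5 to 6 |
| b = 5/3 = 1.67 up to 5 | 5 | just above 5 to 6 |

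Below the lower limit the product text does not call for stopping on this criterion.

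**2. One case followed through the protocol (illustrative).** An adult with normal baseline liver function and no response has ALT of 4 x ULN with raised direct bilirubin at week 4.

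- 10.3.1: discontinue.
- 5.3.2: no repeat test and no hold, because 4 is not above 6.
- 8.6.2, persistent hepatotoxicity: not met, because it is defined by 5.3.2.
- 8.6.2, Grade IV: covers related Grade IV toxicity only, and leaves out laboratory changes that reverse readily.
- 8.6.2, intolerance: applies after dose reduction has failed, and names no liver value.
- 8.6.2, ineligibility: worded for disease progression or a concomitant condition. It could be read with the entry limit of 2.0 mg/dL for bilirubin in 4.2.6, but it does not pair ALT with direct bilirubin.
- 5.2: the table says to increase by 50 mg.
- 2.6: escalation depends on tolerance, which is not defined for the liver.
- 9.2.1: the investigator may interrupt drug, but need not.

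**3. Exposure to the gap.** Escalation points: (300 - 150)/50 = 3, and for East Asian adults (150 - 75)/25 = 3, at weeks 4, 8 and 12.

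**4. Whether the data exist to apply a rule.** Appendix B lists ALT with total and direct bilirubin at weeks 2, 4, 6, 8, 10, 12, 14 and 16, which is 8 panels. Weeks 18 and 20 make 10 for subjects who continue. In extended access on drug the panel is two-weekly. The two-weekly lists in 6.2 and 6.3 ask for total or direct bilirubin, so a site working from those lists could omit the direct value.

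**5. Whether the existing restart rule can serve a new hold.** It cannot. A subject held at 4 x ULN is already below the 5 x ULN restart level on the day of the hold. The new hold needs its own restart condition.

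**The case against.** The strongest reply is that the instruction is already in the protocol. Section 10.3.1 is current text in imperative form. It asks for fractionation of raised bilirubin, repeat testing within 3 to 5 days, and discontinuation for exactly this pattern. Add the tolerance condition for escalation, the investigator's freedom to interrupt, review of outside results by the principal investigator and the intolerance criterion, and a careful investigator would stop. This stands in part: what is missing is a required hold, not the ability to hold. But 10.3.1 is reproduced as risk information, and the section that governs dosing does not refer to it.

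A second reply is selectivity: if leaving out the progressive-rise and four-week qualifiers is an acceptable choice, why not the other two? Those two concern the course of ALT itself and belong with the choice of an ALT-only threshold. Direct bilirubin and clinical signs are separate evidence that no ALT threshold can capture, and the documents give no reason for setting them aside.

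Third, the practical yield may be small. Section 2.4.6 describes earlier liver enzyme elevations as generally asymptomatic and reversible, and 10.3.1 says the severe cases resolved off drug. The note on sachets in 5.1 suggests, by inference only, that enrolment was over by this amendment. That weakens the escalation argument, but extended access continues while response lasts and permits re-initiation (5.5).

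A reader might infer more: that the 6 x ULN limit is itself an error, that the trial breaches a binding rule, or that subjects were harmed. The documents support none of these. A limit of 6 x ULN with restart below 5 x ULN fits an entry limit of 5 x ULN. The product text is not presented as this trial's dosing rule. No trial data on the joint pattern are given; the 12% with increased transaminases among 43 patients in the severe aplastic anemia trial says nothing about accompanying bilirubin.

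**Conclusion.** The point holds as a gap in a required safety action. For ALT from the 10.3.1 floor up to 6 x ULN, with increased direct bilirubin or clinical liver injury, the dosing section requires neither a repeat test nor a hold, while the risk section says to discontinue. The band is 3 x ULN wide with normal baseline and about 1 x ULN wide when baseline is 1.67 x ULN or more. The number of subjects who would fall in it cannot be derived from the documents and may be zero.

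The conclusion assumes that 5.3.2, rather than 10.3.1, is what sites follow for dosing. If sites treated 10.3.1 as binding, the remaining defect would be two sections giving different instructions, which the same edit cures. Efficacy inference, sample size and error rates are untouched. The change should be made because it is cheap and concerns patient safety; confidence is medium.

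**What to change.** 1. Add to section 5.3.2, in words to this effect: *Regardless of the >6 x ULN rule, hold eltrombopag and do not escalate if ALT is >=3 x ULN (with raised baseline: >=3 x baseline or >5 x ULN, whichever is lower) and is accompanied by direct bilirubin above the ULN and above baseline, or by clinical signs of liver injury or hepatic decompensation. Repeat liver tests within 3 to 5 days. The <5 x ULN restart does not apply to this hold. Restart, at the reduced dose given in this section, only if ALT is below the triggering limit, direct bilirubin has returned to baseline or normal, signs have resolved, and benefit is judged to outweigh risk (section 10.3.1). Discontinue permanently on recurrence.*

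2. In the two-weekly lists of 6.2 and 6.3, ask for total *and* direct bilirubin, to match Appendix B.

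The criterion uses direct rather than total bilirubin because the drug may itself raise the indirect fraction. Requiring a value above both the ULN and baseline keeps a long-standing elevation from triggering the hold.

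Cost: one short paragraph and two one-word edits, with no added scheduled visits or scheduled tests. The 3-to-5-day repeat arises only after a hold. The downside is possibly a few more dose interruptions. The ALT-only stop at >6 x ULN and its <5 x ULN restart are left as they are.

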2.6 Rationale for dose selection

Dose selection prior to January 8, 2015:

Eltrombopag 50 mg once daily has been selected as the starting dose for this study because this regimen has been safe and effective in increasing platelet counts in patients with ITP and this was the FDA's recommended starting dose for this patient population. A starting dose of 25 mg once daily in East Asian patients will be used. Modified dosing for subjects of East Asian heritage (i.e., Japanese, Chinese, Taiwanese and Korean) has been implemented for the following reasons. In healthy Japanese subjects, plasma eltrombopag $AUC_{(0-\tau)}$ was approximately 80% higher when compared to non-Japanese healthy subjects who were predominantly Caucasian. Similarly, in patients with ITP, plasma eltrombopag exposure was approximately 70% higher in East Asian (i.e., Japanese, Chinese, Taiwanese and Korean) subjects as compared to non-East Asian subjects who were predominantly Caucasian as higher drug exposure in East-Asian subjects has been observed. After two weeks, the dose can be increased by 25 mg per day every 2 weeks in incremental doses up to a maximum dose of 300 mg (East Asians 125 mg) once daily as detailed in the treatment plan (Section 5) based on the following considerations:

- In an ongoing open label study (NCT00358540), eltrombopag doses of 75 mg (n=10), 100 mg (n=6) and 150mg (n=2) have also been given to patients receiving adriamycin and ifosfamide (AI) for the treatment of advanced soft tissue sarcoma. Dose escalations to 300 mg are planned in this ongoing study. Eltrombopag is being dosed daily for 5 days before and 5 days after AI chemotherapy starting in Cycle 2. [There were 4 patients who were dosed at 100mg. Two of the four had improved numeric platelet counts at the nadir in the cycle that they received eltrombopag compared to the cycle without eltrombopag. All had higher prechemotherapy platelet counts in Cycle 2 (with eltrombopag) compared to Cycle 1 (no eltrombopag). The one subject dose at 150mg did not take the tablets according to instructions]
- In healthy subjects, a clear dose and exposure response was seen for eltrombopag doses of 10 mg to 200 mg once daily for 5 days, with geometric mean $AUC_{(0-\tau)}$ values of 302 $\mu\text{g}\cdot\text{h}/\text{mL}$ for the 200 mg once daily regimen. Eltrombopag was well tolerated in healthy subjects at all dose levels.

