5.0 TREATMENT PLAN

5.1 Administration of study drug (eltrombopag)

Note: Currently sachets are not available, and the manufacturer is working on a new formulation. However, information regarding the use of sachets for children 2-5 years of age or older children unable to take pills is no longer applicable, because the study did not enroll any subjects that required use of the sachets.

Prior to January 8, 2015

Subjects will initiate study drug at 50mg orally once a day, taken on an empty stomach one hour before or at least two hours after a meal as detailed in section 5.9. Subjects of East Asian ancestry (Japanese, Chinese, Taiwanese and Korean) will initiate study drug at 25 mg orally once a day.

After January 8, 2015

Subjects will initiate study drug at 150 mg orally once a day, taken on an empty stomach one hour before or at least two hours after a meal as detailed in section 5.9. Subjects of East Asian ancestry (Japanese, Chinese, Taiwanese and Korean) will initiate study drug at 75 mg orally once a day. Pediatric patients will be treated in a separate cohort with a fixed dose (see Pediatric Dosing table below in section 5.2 and section 10.2).

5.2 Dose Escalation of Eltrombopag Through Primary Endpoint at 16-20 Weeks (See section 2.5)

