Patients will be enrolled on study because of anemia and/or thrombocytopenia. The majority of patients are expected to have cytopenias in both lineages, however some patients will have normal or close to normal counts in one or the other lineage at baseline. Therefore, dose escalation criteria will vary depending on whether one or both lineages meet inclusion criteria. Escalation will occur via the tables below and continue to the maximum dose until the inclusion criterion lineage or lineages responds, according to the schema set out below, unless toxicity-related stopping or dose reduction lab values occur. Note that patients entering the study based on anemia, with normal or near normal platelet count, will be expected to have an increased in their platelet count on eltrombopag, but dose escalation for anemia will not be halted unless the platelet count goes above 400,000/uL. For patients entering meeting both anemia and thrombocytopenia eligibility criteria, dose escalation will not stop until both lineages reach the thresholds given below to stay on the current dose, unless platelets go over 400,000/uL or hemoglobin goes over 16.0 gr/dL, in which case drug will be discontinued for one week and the dose decreased by 50%.

Dose Escalation for Patients Entering with Platelets <30,000/uL or transfusion-dependence:

Platelet Count < 30,000/uL or transfusion-dependent at baseline	Dose Adjustment or Response
<20,000/uL above baseline	Increase daily dose by 50 mg (25 mg for East Asians) every 4 weeks to maximum 300 mg/day for non- East Asians (150 mg/day for East Asians).
≥20,000/uL above baseline but ≤200,000/uL following at least 2 weeks of eltrombopag	Keep at current dosage.
>200,000/uL (untransfused) at any time on	Decrease dosage by 50 mg (25

Platelet Count < 30,000/uL or transfusion-dependent at baseline	Dose Adjustment or Response
study	mg for East Asians) every 4 weeks to lowest dosage that maintains platelet count $\geq 20,000/uL$ above baseline.
>400,000/uL (untransfused) at any time on study	Discontinue eltrombopag for one week, if platelets < 20,000/uL; restart at 50% of current dose.

Dose Escalation for Patients Entering with Anemia (Hb < 8.5gr/dL or transfusion-dependence)

Hemoglobin < 8.5 gr/dL or transfusion dependent at baseline	Dose Adjustment or Response
Hemoglobin rise of < 1.5 g/dL.	Increase daily dose by 50 mg (25 mg for East Asians) every 4 weeks to maximum 300mg/day for non- East Asians (150mg/day for East Asians).

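### The liver-toxicity restart rule in section 5.3.2 gives 0 mg at 50 mg/day and a negative dose at 37.5 mg/day, two levels the protocol itself uses and its one low-dose exception does not cover

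*Combined protocol and SAP*

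**What the plan says.** Section 5.3.2 sets one rule for all patients. If a repeat test confirms ALT above 6 times the upper limit of normal, eltrombopag is held until ALT is below 5 times that limit. Then: "Eltrombopag will be restarted at a dose level 50 mg/day lower than the prior dose". One low dose is treated separately: "If the toxicity appeared on a dose of 25 mg/day, eltrombopag will be discontinued permanently". Recurrence is judged at the lowered dose: "If liver test abnormalities return to an ALT of > 6 times ULN on this reduced dose, eltrombopag will be permanently discontinued".

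The dose levels are set elsewhere:

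- **Current adult start (section 5.1).** "Subjects will initiate study drug at 150 mg orally once a day", with 75 mg for East Asian subjects.
- **Start before 8 January 2015 (section 5.1), now superseded.** "Subjects will initiate study drug at 50mg orally once a day"; East Asian subjects "will initiate study drug at 25 mg orally once a day". Section 2.6 adds that "the dose can be increased by 25 mg per day every 2 weeks".
- **Escalation (section 5.2 tables).** "Increase daily dose by 50 mg (25 mg for East Asians) every 4 weeks to maximum 300 mg/day".
- **Reductions (sections 5.2 and 5.4.3).** High platelets bring 50 mg steps down (25 mg for East Asian subjects). Very high platelets, or high hemoglobin, bring a 50% cut.
- **Extended access (section 5.5).** Once counts stabilize after the drug is re-started, it may be tapered in 50 mg steps to the lowest effective dose.
- **Children (table in section 5.2).** Fixed doses of 150, 75 or 37.5 mg by age and ancestry, and weight-based doses at ages 2-5.

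The off-study list in section 8.6.2 includes persistent hepatotoxicity, defined by reference to 5.3.2.

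**The concern.** A fixed subtraction of 50 mg works only above 50 mg/day. The exception names 25 mg/day alone, although other levels at or below 50 mg/day appear in the dosing sections. At those levels the rule orders a restart but returns no dose to restart at.

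The rule governs a toxicity that carries a boxed warning (section 10.3.1). The adverse-reaction table in that section lists increased transaminases, of any degree, in 12% of 43 patients in the severe aplastic anemia trial, so the rule may well be invoked. What hangs on it is whether a patient goes back on drug or stops permanently and leaves the study under 8.6.2. That decision should not vary from one treating physician to another.

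**Working it through.** The plan states no figure to reproduce. The check applies the rule to each dose level in the documents.

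Formula: restart dose = prior dose - 50 mg/day.

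| Prior dose (mg/day) | Where it comes from | Restart dose (mg/day) | Status |
|---|---|---|---|
| 300 | Maximum, non-East Asian (5.2) | 300 - 50 = 250 | Can be followed |
| 150 | Current adult start (5.1); East Asian maximum (5.2); non-Asian age 12-18 | 150 - 50 = 100 | Can be followed |
| 75 | Current East Asian adult start (5.1); non-Asian age 6-11; East/South East Asian age 12-18 | 75 - 50 = 25 | Can be followed |
| 50 | Reached by reduction; superseded pre-2015 start | 50 - 50 = 0 | No restart dose, no stop stated |
| 37.5 | East/South East Asian age 6-11; 75 mg halved | 37.5 - 50 = -12.5 | No restart dose, no stop stated |
| 25 | Superseded East Asian start; also reachable by reduction | Not applied | Permanent stop stated |

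**Can 50 mg/day still occur?** Yes, by several routes in the current text:

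- 150 - 50 - 50 = 50, through the platelet reductions in 5.2 or the taper in 5.5.
- 75 - 25 = 50, through one East Asian platelet reduction in 5.2.
- 100 × 0.5 = 50, through the halving in 5.2 or 5.4.3.

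Under the superseded scheme it was the adult start, and the second East Asian step (25 + 25 = 50).

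**Can 37.5 mg/day occur?** It is a row of the current pediatric table. It also follows from 75 × 0.5 = 37.5 under 5.2 or 5.4.3.

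**Would the trigger be seen at these doses?** Section 6.3 measures ALT every two weeks on drug during extended access, where section 3.0 calls for the lowest dose that keeps counts stable. Section 8.6.2 applies in that phase too.

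**Ages 2-5.** At 2.5 mg/kg the result is zero or negative up to 50 / 2.5 = 20 kg. At 1.25 mg/kg it is so up to 50 / 1.25 = 40 kg, apart from a dose of exactly 25 mg, which the exception covers. These rows carry little practical weight, because section 5.1 reports that no enrolled subject needed the sachets and section 11.1 supplies this age group by sachet.

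**East Asian variant.** The fixed-mg steps in the 5.2 tables have a 25 mg East Asian version. Section 5.3.2 has none. The 50% reductions and the 5.5 taper have none either.

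**The case against.** The best reply is that zero means stop. Taking 50 from 50 leaves no drug, and the sentence on 25 mg shows the intent that a patient with no room to reduce comes off permanently. Section 8.6.2 also lists intolerance not resolved by dose reduction, and section 9.2.1 lets the investigator interrupt dosing at discretion.

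This reading is reasonable, but it is inferred. The text orders a restart, then speaks of recurrence at the reduced dose, and states a permanent stop for 25 mg only. The hepatotoxicity criterion in 8.6.2 sends the reader back to 5.3.2. The permission to interrupt sets no restart dose. At 37.5 mg/day the subtraction is negative and has no literal meaning.

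The objection on reach stands. The 50 mg starting dose is superseded, and the usual current doses give workable results.

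Three stronger readings may tempt a reader, and the documents do not support them:

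- **That 5.3.2 alone fails to scale for East Asian subjects.** The 50% cuts and the 5.5 taper are unscaled as well. Section 2.4.6 reports hepatobiliary abnormalities in 15.8%, 16.7% and 20.8% of Asian subjects against 10.2%, 7.5% and 4.5% of White subjects in three studies. That makes clear wording more important, but it does not show that a particular step is wrong.
- **That the uneven proportional cut is an error.** The cut is 50/300 = 17%, 50/150 = 33% and 50/75 = 67%. Each leaves a positive dose, so there is no contradiction. Whether a fixed step is suitable is a clinical judgment.
- **That 25 mg/day also fails.** The text covers it.

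**Conclusion.** The point holds in a narrow form. Section 5.3.2 gives 0 mg at 50 mg/day and -12.5 mg at 37.5 mg/day. Both levels occur under the current protocol, and neither is covered by the 25 mg exception. This is an inconsistency between a stated safety rule and the protocol's own dose levels, not merely a missing detail.

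The reach is probably small, and the documents do not give a count. For the pediatric row a rough bound is possible. Section 10.1 expects 15% of patients under 18 and 6% Asian. If the two are independent and apply to the maximum of 38 subjects in section 8.3, then 38 × 0.15 × 0.06 = 0.34, or about 0.3 Asian children of any age and fewer aged 6-11. The other affected patients would be those reduced to 50 or 37.5 mg/day who then have a confirmed ALT above the threshold; their number cannot be derived. No sample-size or stopping-boundary figure changes.

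**What to change.** Reconcile section 5.3.2 with the dose levels in 5.2, the pediatric table, 5.4.3 and 5.5, so that every level in use has either a restart dose that can be given or an explicit instruction to stop. Make clear whether East Asian and pediatric subjects follow the same rule. The hepatotoxicity criterion in 8.6.2 would then be settled at every dose level. Which rule applies is for the sponsor and investigator to decide. The cost is an amendment of wording; the analysis and sample size are untouched.
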